4.2.4 Hepatic Non-Hematologic Dose Limiting Toxicity

- Any Grade 3 elevation of one or more Please see **Section 6.5.2.2** for further management guidelines.
- A Grade 3 elevation of total bilirubin. Please see **Section 6.5.2.2** for further management guidelines.
- Any event meeting the criteria for Hy's law as follows (all three features):
 - Aspartate aminotransferase (AST) and/or alanine aminotransferase (ALT) $> 3 \times$ ULN.
 - Concurrent elevation of total bilirubin $> 2 \times$ ULN without initial evidence of cholestasis (e.g., elevated serum alkaline phosphatase [ALK-P])
 - No alternative etiology can be identified.

4.3 Dose Escalation Rules

The **Dose Escalation Phase (Part A)** of this trial will proceed using a conventional 3 + 3 approach, and will begin with enrollment of 3 patients at a dose of 200 mg pembrolizumab administered as an IV infusion once every 3 weeks and an initial dose of 10 mg/kg margetuximab administered as an IV infusion once every 3 weeks. Successive dose escalation cohorts will be enrolled as outlined below. The MTD or MAD will be determined based on the assessment of DLTs during the DLT Evaluation Period. Patients who are not evaluable for safety for the full DLT evaluation period for reasons other than study drug-related toxicity will be replaced in the same dose-level cohort.

- If 0 of the first 3 patients treated at a given dose level experience a drug-related DLT during the DLT evaluation period, the dose will be escalated and 3 patients will be enrolled and treated at the next higher dose level.
- If 1 of the first 3 patients treated at a given margetuximab dose level experiences a drug-related DLT, then 3 additional patients will be enrolled at that dose level (thus making a total of 6 patients in this cohort) to further assess the safety of the combination.

- If ≥ 1 of these 3 additional patients enrolled in the cohort experience a DLT (that is, ≥ 2 out of 6), it will be concluded that the MTD has been exceeded, and 3 patients will be enrolled and treated at the next lower dose level. If 0 of the 3 additional patients experiences a DLT (that is only 1 of 6 patients has experienced a DLT), then the dose will be escalated, and 3 patients will be enrolled at the next higher dose level.
- If ≥ 2 patients out of the first 3 patients treated at a given dose level, or ≥ 2 of 6 patients treated at a given dose level, experience a drug-related DLT, then it will be concluded that the MTD for margetuximab in combination with pembrolizumab has been exceeded at that dose level, and all subsequent patients will be treated at the next lower dose level.
- Note that in the circumstance in which a DLT occurs during or immediately following the first pembrolizumab infusion and before the first margetuximab administration, the toxicity will be attributed to pembrolizumab alone and will not count as a DLT of the combination of study drugs at the dose level under study. In this case the patient will be replaced by another patient in the dose cohort.
- A total of 6 patients were treated at the RP2D prior to enrolling in the Cohort Expansion Phases of the study.

Following these rules for dose escalation, the MTD/MAD for the combination of margetuximab and pembrolizumab will be defined as the dose level at which $< 33\%$ of patients experience a drug-related DLT during the DLT evaluation period. If no MTD is defined for the combination of margetuximab and pembrolizumab after escalation to the maximum protocol-specified dose, that dose level will be designated as the MAD.

Dose escalation to the next dose level is permitted only after the patients enrolled in the current dose cohort have completed the DLT evaluation period and safety data have been reviewed.

At the discretion of the Sponsor, dose escalation may be stopped before an MTD is reached. In this case, the MAD may be chosen based on an assessment of PK, PD, biomarker, safety, and response data. An MTD does not have to be reached to expand a dose cohort if the available data demonstrate that a lower dose level may provide antitumor activity while minimizing potential risk.

4.4 Rules for Treatment Discontinuation

Patients who tolerate treatment with pembrolizumab and margetuximab may continue to receive additional treatment with the study drugs as specified in the protocol (see [Section 4.1.1](#)), until any one of the following conditions are met:

- After documentation of a confirmed complete response (cCR), the combination of margetuximab and pembrolizumab is continued for one more treatment cycle.
- Patient meets criteria for immune-related disease progression (irPD) ([Appendix 8](#))
- Occurrence of drug-related DLT

- The Sponsor, investigator, or regulatory agency terminates the study
- Withdrawal of patient due to an AE or SAE
- Withdrawal of patient consent
- Completion of protocol defined therapy
- Investigator discretion
- Pregnancy
- Death
- Two years of pembrolizumab and margetuximab combination treatment

4.5 Guidelines for Dose Modifications

No intra-patient dose escalation will be allowed. No dose reductions will be allowed. Infusion rate reduction is allowed during re-challenge for patients experiencing an infusion reaction ([Section 6.5.1](#)). Patients who experience a DLT that is considered related to either study drug should be withdrawn from further pembrolizumab or margetuximab administration but will be followed-up for safety purposes.

4.5.1 Dose Delays

Patients who experience toxicity that is potentially dose-limiting should have study drug held pending assessment, management, and resolution of the toxicity. Specific guidance for the management of known toxicities associated with pembrolizumab and margetuximab treatment, including infusion-related reactions, immune-related adverse events (irAEs), and cardiotoxicities of special interest is provided in [Section 6.5](#). For patients in whom the toxicity is assessed to be unrelated to study drug or for whom the toxicity does not meet the criteria for DLT or meet criteria for the known toxicities, therapy may be re-instituted at the same dose and schedule that was administered prior to the event, presuming the toxicity has resolved to \leq Grade 1 in severity. Reinstitution of therapy shall be conducted as follows:

- For patients in whom the toxicity is assessed to be related to study drug, dose delays of up to 14 days are allowed (see exception for cardiotoxicities of special interest described in [Section 6.5.3](#)). This may include up to one missed dose. However, the procedures at the original scheduled missed visit should be performed as soon as possible and resumed as Day 1 of next cycle with treatment reinstated after recovery from toxicity.
- For patients in whom the toxicity is assessed to be related to study drug, dose delays $>$ 14 days will result in discontinuation of treatment (see exception for cardiotoxicities of special interest described in [Section 6.5.3](#)).

4.6 Rationale for Study Design

As described in [Section 2.4](#), there is a strong rationale to evaluate the antitumor activity of the margetuximab and pembrolizumab combination in HER2+ GEJ and GC. The study is designed to determine the MTD or MAD (if no MTD is defined) of the combination in the Dose Escalation Phase (Part A) of the study. The DLT Evaluation period occurs within the first 3-week treatment cycle; patients who do not experience a DLT or other unacceptable toxicity, or clinically significant progressive disease (PD) (i.e., immune-related progressive disease [irPD]), will then be allowed to continue receiving combination margetuximab and pembrolizumab for up to two years. Once an MAD or MTD is defined, patients will be enrolled into a Cohort Expansion Phase. In this portion of the study, the combination of margetuximab and pembrolizumab will be evaluated in up to 85 evaluable patients (60 patients with relapsed/refractory unresectable locally advanced or metastatic HER2+ GEJ or GC enrolled in Part B [30 each in North America and Asia], and 25 patients in North America and/or Asia with unresectable locally advanced or metastatic HER2+ (IHC 3+) GC enrolled in Part C, using the MAD or MTD determined in the Dose Escalation Phase (Part A).

4.7 Study Duration

Margetuximab and pembrolizumab will be administered in combination once every 3 weeks for up to 2 years. It is expected that enrollment of Part A of the study will occur over approximately 6 months and that enrollment of Parts B - C of the study will take approximately 9-18 months.

The total time for conduct of the trial is expected to be approximately 60 months. These estimates of the timing for study conduct may vary from that observed in the actual conduct of the trial.

4.7.1 Patient Accrual

The number of patients enrolled in **the Dose Escalation Phase (Part A)** cannot be precisely determined in advance and could range up to 12 patients depending on results in the course of the trial and the number of margetuximab doses explored. This patient number does not take into account patient replacement for non-evaluable patients.

The **Cohort Expansion Phases (Parts B – C)** of the trial will enroll up to 85 patients. This includes 30 patients in North America and 30 patients in Asia with relapsed/refractory unresectable locally advanced or metastatic HER2+ GEJ or GC (Part B), and 25 additional patients in North America and/or Asia with unresectable locally advanced or metastatic HER2+ (IHC 3+) GC (Part C).

4.7.2 Definition of End of Trial

The end of study will occur after the last patient completes the **Efficacy Follow Up Period** (see [Section 4.1.4](#)) and the data collection process is complete (time of study database lock).

5 SELECTION AND WITHDRAWAL OF PATIENTS

Inclusion and exclusion criteria are designed to properly define the target population for study participation and to identify those patients who may not be appropriate candidates for study participation based on specific co-morbidities or other clinicopathologic features of their disease. Patients must meet all the inclusion criteria; patients will be excluded from the study if they meet any exclusion criteria. No exceptions to these criteria will be granted by the Sponsor.

5.1 Inclusion Criteria

General:

1. Ability to provide informed consent and documentation of informed consent prior to initiation of any study-related tests or procedures that are not part of standard-of-care for the patient's disease. Patients must also be willing and able to comply with study procedures, including the acquisition of specified research specimens.
2. Age \geq 18 years old (minimum age dependent upon local regulations).
3. Patients may be male or female.
4. **Sixty patients in Part B:** Have histologically proven unresectable locally advanced or metastatic HER2+ gastroesophageal junction (GEJ) or gastric cancer (GC) determined as 3+ by IHC or 2+ by IHC and in situ hybridization– (ISH-) amplified (≥ 2.0) (as per College of American Pathologists/American Society of Clinical Oncology 2016 Guidelines) in most recent tumor biopsy.

Twenty-five patients in Part C (GC only): As of Amendment 2, up to 25 additional patients will have histologically proven unresectable locally advanced or metastatic HER2+ GC (as defined in AJCC Cancer Staging Manual, 8th Edition) determined as 3+ by IHC (as per College of American Pathologists/American Society of Clinical Oncology 2016 Guidelines) in the most recent tumor biopsy.

5. Have received prior treatment with trastuzumab.
6. Have received treatment with one line of cytotoxic chemotherapy in the metastatic setting, which includes trastuzumab. Prior adjuvant therapy that resulted in relapse within 6 months of completion of therapy will be considered a line of treatment for metastatic disease. Eligible patients must have documented progression on/after the most recent line of therapy. Patients who discontinue trastuzumab for other reasons (e.g., financial) are eligible if they have documented progression on/after trastuzumab without receiving alternate treatment.
 - In Parts B and C, only one prior line of treatment that includes trastuzumab is allowed.
7. Resolution of all chemotherapy or radiation-related toxicities to \leq Grade 1 (with exception of \leq Grade 2 alopecia, stable sensory neuropathy, or stable electrolyte disturbances that are managed by supplementation).

8. Eastern Cooperative Oncology Group (ECOG) performance status of 0 or 1 (**Appendix 6**).
9. Life expectancy \geq 12 weeks.
10. Measurable disease as per Response Evaluation Criteria in Solid Tumors (RECIST) 1.1 (**Appendix 7**) and documented by computed tomography (CT) and/or magnetic resonance imaging (MRI). Patients with evaluable disease only will not be enrolled on this study. Note: Lesions to be used as measurable disease for the purpose of response assessment must either a) not reside in a field that has been subjected to prior radiotherapy, or b) have demonstrated clear evidence of radiographic progression since the completion of prior radiotherapy and prior to study enrollment.
11. Patients should have a formalin-fixed, paraffin embedded tumor specimen or unstained slides identified and available for analysis, to enable determination of the expression of HER2 and PD-L1 within tumor specimens using IHC staining.

Laboratory Features:

12. Acceptable laboratory parameters as follows:
 - a. Platelet count $\geq 100 \times 10^3/\mu\text{L}$ without transfusion within 2 weeks prior to the initiation of study drug.
 - b. Absolute neutrophil count (ANC) $\geq 1.5 \times 10^3/\mu\text{L}$ in the absence of any growth factor support within 2 weeks prior to the initiation of study drug.
 - c. Hemoglobin (Hgb) ≥ 9 g/dL.
 - d. ALT/AST $\leq 3.0 \times \text{ULN}$; for patients with hepatic metastases, ALT and AST $\leq 5 \times \text{ULN}$.
 - e. Total bilirubin $\leq 1.5 \times \text{ULN}$, except patients with Gilbert's syndrome, who may enroll if the conjugated bilirubin is within normal limits.
 - f. Creatinine < 2 mg/dL, or a calculated or measured creatinine clearance > 50 mL/min.

Reproductive Features:

13. Female patients of childbearing potential (not surgically sterilized and between menarche and 1 year postmenopause) must have a negative urine pregnancy test performed within 72 hours prior to the initiation of study drug administration. Further, female patients of childbearing potential must agree to use highly effective contraceptive measures from the time of consent through 120 days after discontinuation of study drug administration.

For Canadian patients only: Female patients of childbearing potential must have a negative pregnancy test prior to every cycle of pembrolizumab.

- Highly effective methods of contraception include hormonal contraceptives, intrauterine device or system, vasectomy, or tubal ligation. If a highly effective method is not achievable then a “double barrier” method is an effective alternative in which the male partner must use a condom with spermicide and the female partner must use a diaphragm or cervical cap concurrently.
14. Male patients with partners of childbearing potential must use barrier contraception. In addition, male patients should also have their partners use another method of contraception from the time of consent through 120 days after discontinuation of study drug administration.
 15. Is not pregnant or breastfeeding, or expecting to conceive or father children within the projected duration of the trial, starting with the prescreening or screening visit through 120 days after the last dose of trial treatment.

Tumor Biopsy

16. At least 20 of the 60 patients enrolled in the Cohort Expansion Phase (Part B) under the Original Protocol and Protocol Amendment 1 must have one lesion considered to be potentially accessible to biopsy and be willing to provide consent for biopsy samples. An attempt at a tumor biopsy of locally accessible lesions will be made for at least 20 of the 60 patients. Tumor lesions used for biopsy should not be lesions used as RECIST target lesions unless there are no other lesions suitable for biopsy. If a RECIST target lesion is used for biopsy, the lesion must be ≥ 2 cm in longest diameter. Tumor biopsies should only be obtained from lesions that are felt to be accessible with acceptable clinical risk in the judgment of the investigator.
 - The 25 patients enrolled into Part C will not be required to have pre- and on-treatment biopsies.
 - Diagnostic biopsy sample performed as standard of care will be collected from all patients on study.

Previous Checkpoint Inhibitor Therapy

17. Patients who have previously received an immune checkpoint inhibitor (e.g., anti-PD-L1, anti-PD-1 anti-CTLA-4) prior to enrollment must have toxicities related to the checkpoint inhibitor resolved to \leq Grade 1 or baseline (prior to the checkpoint inhibitor) to be eligible for enrollment.

5.2 Exclusion Criteria

1. Patients with symptomatic central nervous system (CNS) metastases must have been treated, be asymptomatic, and meet the following at the time of enrollment:

- a. No concurrent treatment for the CNS disease (e.g. surgery, radiation, corticosteroids ≥ 10 mg prednisone/day or equivalent).
 - b. No progression of CNS metastases on MRI or CT for at least 21 days after last day of prior therapy for the CNS metastases.
 - c. No concurrent leptomeningeal disease or cord compression.
2. Patients who experienced the following immune checkpoint inhibitor-related AEs (i.e., the following AEs make the patient ineligible despite the AE resolving to \leq Grade 1 or baseline):
 - a. \geq Grade 3 ocular AE.
 - b. Changes in liver function tests that met the criteria for Hy's Law ($> 3 \times$ ULN of either ALT/AST with concurrent $> 2 \times$ ULN of total bilirubin and without alternate etiology).
 - c. \geq Grade 3 neurologic toxicity.
 - d. \geq Grade 3 colitis or pneumonitis.
 3. Patients with any history of known or suspected autoimmune disease with the specific exceptions of vitiligo, resolved childhood atopic dermatitis, psoriasis not requiring systemic treatment (within the past 2 years) and patients with a history of autoimmune disease that are now clinically stable with replacement therapy and by laboratory testing.
 - a. Patients with history of psoriatic arthritis are excluded.
 4. History of prior allogeneic bone marrow, stem-cell or solid organ transplantation.
 5. Treatment with any systemic anti-neoplastic therapy, or investigational therapy within the 3 weeks prior to the initiation of study drug administration. Adjuvant hormonal therapy for treatment of prostate or breast cancer is allowed.
 6. Treatment with radiation therapy within 3 weeks prior to the initiation of study drug administration.
 7. Treatment with corticosteroids (≥ 10 mg per day prednisone or equivalent) or other immune suppressive drugs within the 14 days prior to the initiation of study drug administration. Steroids for topical, ophthalmic, inhaled or nasal administration are allowed.
 8. History of clinically significant cardiovascular disease including but not limited to:
 - a. Myocardial infarction or unstable angina within the 6 months prior to the initiation of study drug.
 - b. Stroke or transient ischemic attack within 6 months prior to the initiation of study drug.
 - c. Clinically significant cardiac arrhythmias.

- d. Uncontrolled hypertension: systolic blood pressure (SBP) >180 mmHg, diastolic blood pressure (DBP) >100 mmHg.
 - e. Congestive heart failure (New York Heart Association [NYHA] class III-IV).
 - f. Pericarditis or clinically significant pericardial effusion.
 - g. Myocarditis.
 - h. Left ventricle ejection fraction (LVEF) < 50% by echocardiogram or multi-gated acquisition (MUGA) scan.
9. Clinically significant pulmonary compromise, including a requirement for supplemental oxygen use to maintain adequate oxygenation.
 10. Has a history of (non-infectious) pneumonitis that required steroids or has current pneumonitis.
 11. Clinically significant gastrointestinal disorders including:
 - a. Any history of gastrointestinal perforation unless the affected area has been deemed by the investigator to no longer be a risk for perforation.
 - b. History of clinically significant gastrointestinal bleeding within 4 weeks prior to the initiation of study drug.
 - c. History of acute pancreatitis within 4 weeks prior to the initiation of study drug.
 - d. Diverticulitis that is clinically significant in the opinion of the investigator based on the extent or severity of known disease and/or the occurrence of clinically significant disease flares within 4 weeks prior to the initiation of study drug administration.
 12. Evidence of active viral, bacterial, or systemic fungal infection requiring parenteral treatment within 7 days prior to the initiation of study drug. Patients requiring any systemic antiviral, antifungal, or antibacterial therapy for active infection must have completed treatment no less than one week prior to the initiation of study drug.
 13. Known positive testing for human immunodeficiency virus or history of acquired immune deficiency syndrome.
 14. Known history of hepatitis B or hepatitis C infection or known positive test for hepatitis B surface antigen, hepatitis B core antigen, or hepatitis C polymerase chain reaction (PCR).
 15. History of another malignancy or a concurrent malignancy. Exceptions include patients who have been disease free for two years, or successfully treated for non-melanoma skin cancer, localized prostate cancer (Gleason Score <6) or carcinoma in situ, for example cervical cancer in situ, are eligible.
 16. History of trauma or major surgery within 4 weeks prior to the initiation of study drug administration.

17. Any serious underlying medical or psychiatric condition that would impair the ability of the patient to receive or tolerate the planned treatment at the investigational site.
18. Known hypersensitivity to recombinant proteins, polysorbate 80 or any excipient contained in the drug or vehicle formulation for margetuximab or pembrolizumab ([Section 6.1](#)).
19. Vaccination with any live virus vaccine within 4 weeks prior to the initiation of study drug administration. Inactivated annual influenza vaccination is allowed.
20. The female patient who is pregnant or breastfeeding, or expecting to conceive, AND the male patient who is expecting to father children within the projected duration of the trial, starting with the screening visit through 120 days after the last dose of trial treatment.
21. Dementia or altered mental status that would preclude understanding and rendering of informed consent.
22. Employees of MacroGenics, Inc., and Merck & Co., Inc., unless approved by institutional IRB and principal investigator.
23. Prisoners or other individuals who are involuntarily detained.
24. Any issue that in the opinion of the investigator, would contraindicate the patient's participation in the study or confound the results of the study.

5.3 Withdrawal of Patient from the Study

If the investigator decides that the patient should be withdrawn from the study or from dosing for any reason other than disease progression, the Sponsor or its designee must be alerted within 24 hours via an Immediately Reportable Event form ([Section 7.9.6](#)).

Patients who withdraw before Study Day 21 during the Dose Escalation Phase (Part A) for a reason unrelated to drug toxicity may be considered to have inadequate data to support dose escalation. In this case, replacement patients may be enrolled in the same dose level.

Procedures for handling patients who fail to appear for study visits and criteria regarding when to consider patients lost-to-follow-up will be defined in the Study Manual.

5.3.1 Guidelines for Study Discontinuation

Patients who are no longer on treatment but are still followed on the study can be terminated from the study for the following reasons:

- Completion of protocol defined follow-up period.
- Uncontrolled intercurrent illness unrelated to cancer that renders continuing study follow-up unsafe or regular study visits impossible.
- The Sponsor, investigator, or regulatory agency terminates the study.
- The patient requests to be discontinued from the study, i.e., withdrawal of consent.
- Noncompliance with protocol-required evaluations.
- The patient exhibits progression of disease (according to irRC).
- Death

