a To be evaluated only if the starting dose is determined to exceed the MTD.

b Starting dose level

An intermediate dose of margetuximab may be explored during the dose escalation portion of the study, based on review of cumulative safety, efficacy, and/or PK data on respective arms and based upon agreement between investigators and Sponsor. The Regulatory Agencies and Institutional Review Boards (IRBs)/Independent Ethics Committees (IECs) will be notified of any additional dose level to be evaluated.

Cohort Expansion Phase (Part B):

The goals for this expansion portion of the study include the following:

1. Provide a preliminary assessment of the antitumor activity of margetuximab in combination with pembrolizumab in patients with relapsed/refractory unresectable locally advanced or metastatic HER2+ GEJ or gastric cancer (GC) post-trastuzumab
2. Further characterize the safety of margetuximab at the MTD (or MAD) in combination with pembrolizumab; and
3. Further evaluate the PK, PD, and immunogenicity of margetuximab in combination with pembrolizumab.

Cohort Expansion Phase - Gastric Cancer Only (Part C):

The goals for the expansion portion of the study include the following:

1. Provide a preliminary assessment of the antitumor activity of margetuximab in combination with pembrolizumab in patients with relapsed/refractory unresectable locally advanced or metastatic HER2+ (3+ by immunohistochemistry [IHC3+]) GC only (as defined in AJCC Cancer Staging Manual, 8th Edition) post-trastuzumab
2. Further characterize the safety of margetuximab at the MTD (or MAD) in combination with pembrolizumab; and
3. Further evaluate the PK, PD, and immunogenicity of margetuximab in combination with pembrolizumab.

Efficacy Follow-up Period:

Following the final dose of study drug (pembrolizumab or margetuximab, whichever is last), each patient will be followed for both PFS and OS during an **Efficacy Follow up Period**. During this time, patients will undergo disease assessments and be followed at 12-week intervals for monitoring of PFS and overall survival.

Dose Limiting Toxicity:

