For patients who are otherwise clinically stable but have met conventional criteria for PD, therapy may be continued at the discretion of the investigator pending confirmation of progression at the next scheduled tumor assessment. This approach allows for limited treatment of patients beyond the initial radiographic documentation of disease progression, assuming that patients are tolerating therapy adequately, that patients remain otherwise clinically stable despite this initial radiographic evidence of disease progression, and that the investigator feels the patient may still derive benefit from continuation of therapy.

For patients in whom progression is confirmed at the next scheduled tumor assessment, the criteria for irPD will have been met, and treatment with margetuximab and pembrolizumab should be discontinued. The patient should be removed from study participation after completion of protocol specified follow-up (see [Section 8.3](#) and [Appendix 1](#) and [Appendix 2](#)).

Efficacy Follow-up Period: Following the last dose of combination therapy, all patients will be followed for PFS and OS for up to 2 years or until 3 months after the last patient completes or discontinues study treatment.

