4.1.4 Efficacy Follow-up Period

Following a patient's final dose of study drug (pembrolizumab or margetuximab, whichever is last), each patient will be followed during the **Efficacy Follow up Period**. The **Efficacy Follow up Period** will end 3 months after the last patient completes or discontinues treatment. During this time, patients will be followed at 12-week intervals for monitoring of progression-free survival and overall survival. Disease assessments should be done at office follow-up visits if patients are agreeable.

Prior to database lock for final OS analysis, survival data will be requested for all patients still in **Efficacy Follow-up Period**, regardless of the interval since the prior assessment.

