8.3 End of Treatment Visit

A list of evaluations to be performed for the End of Treatment visit is provided in [Appendix 1](#) and [Appendix 2](#). Criteria for triggering the End of Treatment visit are specified in [Section 5.3](#). The End of Treatment Visit should be performed after the patient has met off-treatment criteria and End of Study should be noted after patient has been followed for at least 28 days after the last dose of study drug depending on ability to follow the patient and duration and severity of ongoing AEs. It is recognized that certain patients (such as those experiencing progression of disease) may be cared for in facilities other than the participating investigational site, may proceed to receive other cancer therapy, and/or may elect not to return to the investigational site. Therefore, this visit is considered optional, but should be carried out whenever possible.

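### Protocol 5.3.1 allows, without requiring, study termination at irRC progression, and this is not reconciled with the plan to follow every patient for overall survival

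*Protocol*

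**What the plan says.** Protocol 5.3.1 opens: "Patients who are no longer on treatment but are still followed on the study can be terminated from the study for the following reasons". The list includes "The patient exhibits progression of disease (according to irRC"), as an item separate from completing the follow-up that the protocol defines. The wording is permissive, and it concerns patients already off treatment, so it is not a treatment-stopping rule; those rules are in section 4.4.

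The survival plan has no exit at progression. In the synopsis, under the Efficacy Follow-up Period, "patients will undergo disease assessments and be followed at 12-week intervals for monitoring of PFS and overall survival". In Protocol 4.1.1, "all patients will be followed for PFS and OS for up to 2 years" or until a study-level end date. Section 4.1.4 follows each patient every 12 weeks to that end date.

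Three further passages bear on the point:

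- For confirmed irPD, 4.1.1 says: "The patient should be removed from study participation after completion of protocol specified follow-up", with references to section 8.3 and to Appendices 1 and 2.
- Section 8.3 says: "End of Study should be noted after patient has been followed for at least 28 days after the last dose of study drug", subject to whether the patient can be followed and to ongoing adverse events. It does not mention survival.
- Before the final OS analysis, 4.1.4 says "survival data will be requested for all patients still in" the Efficacy Follow-up Period.

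SAP 5.1.2 censors OS at the date a patient was last known alive. SAP 6.6.2.3 estimates median OS and the 1- and 2-year rates.

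**The concern.** Because progression is listed apart from completed follow-up, the bullet adds something only if it lets a patient leave before follow-up is complete. No passage says that survival contact continues after such a termination. A site relying on 5.3.1 could therefore close out a patient whom 4.1.1 and 4.1.4 expect to be followed until death or the end of the study.

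That patient's OS would be censored soon after progression, which is potentially informative because progression and death are related. The pre-lock request might not recover the death, since a terminated patient can be read as no longer in follow-up. Deaths and patients at risk would be lost from the 1- and 2-year OS estimates. The SAP plans a sensitivity analysis for PFS but none for OS.

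**Working it through.** The documents give no figure to reproduce. The check is a comparison of the text, followed by an illustration of size.

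**Text.** Sections 4.1.1 and 4.1.4 set a duty covering all patients. Section 5.3.1 gives a permission. Both can be honoured only if the permission is not used. Whether the pre-lock request reaches terminated patients is open: 4.1.4 ends the Efficacy Follow-up Period at a study-level date, so a terminated patient could be counted in or out.

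**Inputs.** From the documents: up to 85 expansion patients (Protocol 9.2), and month 24 as the last OS time point (SAP 6.6.2.3). Assumed: exponential times, median PFS 2.7 months, median post-progression survival 8 months, 15% of PFS events being deaths, exit 6 weeks (1.4 months) after progression for a share f of progressors, and otherwise complete follow-up.

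**Hazards per month.**
- PFS event: L = ln 2 / 2.7 = 0.2567
- Death without progression: 0.15 × L = 0.0385
- Progression: a = 0.85 × L = 0.2182
- Death after progression: d = ln 2 / 8 = 0.0866

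**Full follow-up.** S(24) = exp(−24L) + [a/(L−d)] × [exp(−24d) − exp(−24L)] = 0.160. Expected deaths are 85 × (1 − 0.160) = 71.4, with 13.6 patients at risk.

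**Deaths that termination can hide.** The chance that a patient progresses, survives 1.4 months more and then dies by month 24 is a × {exp(−1.4d) × [1 − exp(−22.6L)]/L − exp(−24d) × [1 − exp(−22.6(L−d))]/(L−d)} = 0.594. Times 85, this is 50.5 deaths, so deaths seen are 71.4 − f × 50.5. Patients at risk at month 24 fall by f × 13.3 in the same way. Median OS is the limiting Kaplan-Meier value.

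| Share of progressors terminated | Deaths seen by month 24 | Lost | At risk at month 24 | Median OS (months) |
|---|---|---|---|---|
| 0% | 71.4 | – | 13.6 | 10.4 |
| 10% | 66.4 | 7% | 12.2 | 10.5 |
| 25% | 58.8 | 18% | 10.2 | 10.7 |
| 50% | 46.2 | 35% | 6.9 | 11.0 |

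In 4,000 simulated base-case trials of 85 patients, the mean width of the log(−log) 95% interval for 1-year OS was 20.7 points with full follow-up, 22.7 at 25% use and 25.6 at 50%. For 2-year OS the widths were 15.2, 17.6 and 21.4 points.

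**Sensitivity.** Sixteen scenarios crossed the base case, the pembrolizumab monotherapy figures in Protocol 2.2.1 (median PFS 1.9, OS 11.4 months) and the weekly paclitaxel ranges in Protocol 2.1.2 (PFS 2.1 to 2.6, OS 5.0 to 7.8 months) with death shares of 10 to 25%. Deaths lost by month 24 were 13–19% at 25% use and 27–38% at 50% use. At 50% use, median OS shifted by −0.6 to +0.8 months. If exit comes 2.8 months after progression, in line with the later 12-week scans, the base case at 50% use gives 49.8 deaths instead of 46.2.

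**Direction of bias.** The sign changes where the death hazards before and after progression are equal, that is, where the death share equals median PFS / median post-progression survival. In the base case this is 2.7/8 = 34%. With the Protocol 2.2.1 figures it is 1.9/11.4 = 16.7%: at 50% use, a median of 11.4 months becomes 11.5 at a 15% share and 11.2 at a 20% share.

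**The case against.** The strongest reply is that survival follow-up after irPD is already the stated plan. The removal sentence in 4.1.1 cites Appendices 1 and 2 as well as 8.3, and both appendices have follow-up columns with telephone, electronic or office contact. In the synopsis, the parallel sentence is followed directly by a statement that each patient is followed for PFS and OS. Section 4.7.2 ends the study only after the last patient completes the Efficacy Follow-up Period. On this view, one loose permissive bullet remains. That largely stands: it rules out a strict contradiction. It does not remove the bullet, and no text says that survival contact outlasts a 5.3.1 termination.

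Three stronger readings are tempting, and the documents do not support them.

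- A reader might infer from section 5.3 that exits at progression would pass unreported, because the 24-hour alert covers patients "withdrawn from the study or from dosing for any reason other than disease progression". The phrase covers stopping dosing as well as leaving the study, the matching item in 7.9.2.6 concerns study drug only, and SAP 6.3.1 already reports end-of-study status for all enrolled patients. The exemption is not evidence of a separate problem.
- A reader might infer that 8.3 ends survival follow-up at 28 days. It sits in the End of Treatment Visit section, sets a minimum and refers to ongoing adverse events, so it most likely means minimum safety follow-up. It does not say so.
- A reader might infer that nearly all progressors would be lost. The bullet is optional, and under Appendix 8 new lesions or non-target growth alone do not define irPD, so not every RECIST progressor meets it.

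It is also fair to say that the usage shares have no documentary basis, that a loss of deaths is built into any early termination, and that rewording 5.3.1 or 8.3 cannot recover patients who have already left. Protocol 2.3.1.1 reports 64 patients treated in this study by 30 September 2017.

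**Conclusion.** The point holds as an unreconciled allowance. Section 5.3.1 permits an exit at irRC progression that the synopsis, 4.1.1 and 4.1.4 do not provide for, and the pre-lock request may not close the gap. The effect is confined to OS, a descriptive secondary endpoint; ORR, response duration and the safety objectives are unaffected.

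Its size depends on how often the option is used, which the documents do not reveal. On the assumed base case, the loss runs from 7% of deaths by month 24 at 10% use to 35% at 50% use, and median OS moves by 0.1 to 0.6 months. The main cost is precision in the 1- and 2-year rates. A claim that OS would be overstated, or understated, is not supported, because the sign turns on the unknown share of PFS events that are deaths. Severity: minor to should-fix.

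**What to change.** Reconcile the sections together:

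- **Protocol 5.3.1:** delete the irRC-progression bullet, or limit it to ending tumor assessments while 12-week survival contact continues. Section 7.10.1.1 already ends scheduled scans at documented progression.
- **Protocol 4.1.4:** extend the pre-lock survival request to every treated patient not known to have died who has not withdrawn consent to follow-up. This is the only change that reaches patients already terminated.
- **Protocol 8.3:** state that an End of Study note at 28 days or later closes safety follow-up, not survival follow-up.
- **SAP 6.6.2.3:** report with the OS analysis the number of patients censored at or within 12 weeks after irPD, beside the disposition data in SAP 6.3.1.

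The cost is a wording amendment, with ethics approval where required, across about 29 institutions, plus one SAP line and some extra survival calls. It is best bundled with the next amendment. The 12-week contacts and the telephone or electronic route already exist, and no treatment rule or primary analysis changes.
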